9.7.5. Effectiveness

The effectiveness of DMF on MS disease activity and disability progression will be based on assessment of relapse-related endpoints and EDSS-based progression-related endpoints, respectively. Effectiveness evaluations will include comparisons to external databases.

MS disease activity will be assessed by evaluating the frequency of relapses over time. These analyses may include the following parameters:

- annualized relapse rate
- time to first relapse
- proportion of patients with relapse
- distribution of the total number of relapses

Disability progression will be assessed by evaluating EDSS evolution over time. These analyses may include the following parameters:

- proportion of patients with progression (defined as at least a 1.0 point increase from a baseline EDSS ≥ 1.0 or at least a 1.5 point increase from a baseline EDSS = 0)
- time to first progression
- proportion of patients with sustained progression for at least 6 months
- time to sustained progression for at least 6 months
- proportion of patients with post-baseline EDSS values greater than certain thresholds (e.g., ≥ 4.0 , >6.5) at any time and sustained for at least 6 months

CONFIDENTIAL

The information contained herein may not be used, disclosed, or published without the written consent of Biogen Idec MA Inc.

[figure not shown]
- proportion of patients whose disability status worsened, stabilized, or improved over time, including an analysis based on values sustained for at least 6 months. Improvement may be defined as a decrease of at least 1.0 point from baseline, a stable condition as a change of ≤ 0.5 point from baseline, and worsening as an increase of at least 1.0 point from baseline.

Annualized relapse rate will be analyzed using a negative binomial model, adjusted for appropriate prognostic factors, and time-to-event endpoints will be analyzed using Kaplan-Meier estimates. Analyses of relapse related and progression related endpoints may also be undertaken for patient subgroups defined by appropriate demographic and/or baseline prognostic factors (e.g., EDSS score).

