9.1.2. Secondary Endpoints

Secondary endpoints will address non-safety related study objectives, as follows:

- DMF prescription and utilization patterns will be evaluated by assessment of prescribed dosing frequency, duration of DMF use, and primary reason for discontinuation of DMF (see Section 9.7.4).
- Effectiveness of DMF on MS disease activity and disability progression will be evaluated by assessment of relapse-related endpoints (e.g., annualized

CONFIDENTIAL

The information contained herein may not be used, disclosed, or published without the written consent of Biogen Idec MA Inc.

relapse rate, time to first relapse, proportion of patients with relapse, and distribution of the number of relapses) and by assessment of EDSS-based disability progression-related endpoints (e.g., proportion of patients with progression and time to first progression), respectively (see Section 9.7.5).

- Changes in health-related quality of life measures will be evaluated over time. Healthcare resource consumption will be evaluated by assessment of endpoints such as number of hospitalizations, emergency room visits, and neurologist visits. Work productivity will be evaluated by assessment of ability to work and time needed away from work due to MS (see Section 9.7.6).

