††**Note**: At sites in the US, physicians will be asked to conduct blood draws for CBC (not more frequently than every 12 months unless indicated per local standard of care) and to record the results. To be consistent with local regulations, physicians in the EU and ROW will be asked to record CBC, liver function, renal function, and urinalysis results *if collected as part of routine clinical practice* (i.e., not specifically performed for the study). Additionally, if a patient discontinues DMF due to an abnormal laboratory test result, physicians will be asked to record all relevant laboratory test results collected during the study (starting with the most recent values prior to initiating DMF) *as part of routine clinical practice*.

[figure not shown]
†††**Note**: In order to assure high reliability of assessments, it is essential to have standardized examinations and consistent definitions for the EDSS. Neurostatus certification is highly recommended for all participating physicians. Physicians will be asked to provide their certification information. If they are not certified, they will be provided a copy of the interactive Neurostatus Training DVD-ROM edited by L Kappos and S Wu, Basel – Switzerland and offered a free-of-charge online certification training (www.neurostatus.net).

††††**Note**: PROs will be available to patients online or on paper to allow completion of the questionnaires outside of the physician's office. However, the questionnaires are to be completed within 1 week (before or after) the scheduled visit. Questionnaires may be completed by a proxy (e.g., family member).

†††††**Note**: Pregnancy status will not be collected for female patients who are enrolled in the study but have not initiated treatment with DMF.

Definition of Relapse

For the purposes of this study, relapses are defined as new or recurrent neurologic symptoms not associated with fever, lasting at least 24 hours. New or recurrent neurologic symptoms that evolve gradually over months are to be considered disease progression, not an acute relapse. New or recurrent neurologic symptoms that occur fewer than 30 days following the onset of a relapse as defined above are to be considered part of the same relapse.

CONFIDENTIAL

The information contained herein may not be used, disclosed, or published without the written consent of Biogen Idec MA Inc.

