⁵ US sites will be asked to conduct blood draws for CBC (not more frequently than every 12 months unless indicated per local standard of care) and to report the results. Physicians in the European Union and Rest of World will be asked to record CBC, liver function, renal function, and urinalysis results, *if collected as part of routine clinical practice*. Additionally, in all regions, if a patient discontinues DMF due to a laboratory abnormality (see Table 7, Continued, below), physicians will be asked to record all relevant laboratory test results collected during the course of the study as part of routine clinical practice.

⁶ When collected as part of routine clinical practice.

⁷ If treatment with DMF is not started on the day of enrollment, the start date should be recorded at the next routine visit.

⁸ PROs may be assessed at a routine visit or online outside of the physician's office, *if consistent with local regulations*. If completed online, PROs should be completed within 1 week (before or after) the scheduled visit.

⁹ SAEs and pregnancy status will not be collected in patients who are enrolled in the study but do not initiate treatment with DMF. SAE and pregnancy status will be collected from the first dose of DMF.

Abbreviations: CBC = complete blood count; EDSS = Expanded Disability Status Scale; EQ VAS = EQ Visual Analogue Scale; MFIS-5 = Modified Fatigue Impact Scale-5; MRI = magnetic resonance imaging; MS = multiple sclerosis; MSIS-29 = Multiple Sclerosis Impact Scale-29 Items; PROs = patient-reported outcomes; SAE = serious adverse event; US = United States; WPAI-MS = Work Productivity and Activity Impairment questionnaire; Multiple Sclerosis.

CONFIDENTIAL

The information contained herein may not be used, disclosed, or published without the written consent of Biogen Idec MA Inc.

Table 7: DMF Study 109MS401: Study Activities (Continued)
Discontinuation of Treatment and/or Premature Study Withdrawal Visit, Chart 2 of 2

Assessments	DMF Discontinuation With Continued Study Participation		Premature Study Withdrawal Visit ¹
	First Routine Visit After Last Dose ²	Subsequent Routine Visits After Last Dose	
Date of and primary reason for discontinuation of DMF, and last prescribed dose	X		X
AEs (including laboratory abnormalities) leading to treatment discontinuation	X		
SAEs ^{3,4}	X		X ⁸
Reports of malignancies only		X ⁴	
CBC with differential ⁵	X	X	X
Other laboratory tests recommended in local label ⁵	X	X	X

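### The example EDSS progression endpoints rest on one unconfirmed rise with no handling of relapse scores, and the 6-month sustained versions are only optional

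*Protocol*

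**What the plan says.** Section 9.1.2 gives, as examples of EDSS-based endpoints, the "proportion of patients with progression and time to first progression", and refers to Section 9.7.5 for detail. The abstract gives the same two examples. Neither place says the progression must be sustained.

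Section 9.7.5 introduces its list of EDSS parameters with "These analyses may include the following parameters". Progression is "defined as at least a 1.0 point increase from a baseline EDSS" of 1.0 or more, or "at least a 1.5 point increase from a baseline EDSS = 0". The same list contains the "proportion of patients with sustained progression for at least 6 months" and the "time to sustained progression for at least 6 months". Two further entries, on EDSS thresholds and on worsened, stable or improved status, also have a 6-month sustained form. Time-to-event endpoints are to be analysed by Kaplan-Meier.

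On the timing of scores, the footnote to the EDSS row of Table 7 (Section 16.1) says: "When collected as part of routine clinical practice". No rule ties an EDSS assessment to the presence or absence of a relapse.

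Section 9.3.2, in defining relapse, says: "New or recurrent neurologic symptoms that evolve gradually over months are to be considered disease progression, not an acute relapse".

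**The concern.** EDSS often rises during a relapse and then falls back. Under the definition as written, one such score is enough to make the patient a progressor, and in the Kaplan-Meier analysis that first progression is final whatever the later scores show. The same clinical event then enters both the relapse results and the disability results, although Section 9.7.5 assigns these to disease activity and disability progression respectively.

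Assessing effectiveness on disability progression is a stated secondary objective (Section 8.2). There is no internal control group, so nothing inside the study shows how much of the reported progression is transient. The protocol recognises that sustained change is informative, since it lists sustained versions, but it does not commit to reporting them and does not give them as endpoints in Section 9.1.2 or the abstract.

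**Working it through.** The protocol states no rate, power or sample size for the EDSS endpoints, so there is no figure of its own to reproduce. The check has two parts.

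**1. The rule applied to two constructed records.**

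| Record | Baseline EDSS | Later scores | Unconfirmed rule | 6-month sustained rule |
|---|---|---|---|---|
| A: relapse with full recovery | 2.0 | 3.5 at month 12 in a relapse; 2.0 from month 18 to 60 | Progressed, time 12 months | Not progressed |
| B: gradual decline, no relapse | 2.0 | 3.0 at month 24 and after | Progressed, time 24 months | Progressed |

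Both have the same status on the two endpoints that Section 9.1.2 gives as examples, and A appears to progress sooner. Only the sustained version separates them.

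**2. Illustrative size.** Every input except follow-up is an assumption:

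- mean follow-up: 17,000 person-years / 5000 patients = 3.4 years (Table 5, Section 9.5)
- relapse rate R: 0.1 to 0.3 per year (assumed)
- share of relapses with an EDSS recorded during the relapse, e: 25% to 50% (assumed)
- share of those scores that meet the threshold, q: 30% to 50% (assumed)

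Share of otherwise stable patients with at least one qualifying relapse score = 1 − exp(−R × 3.4 × e × q).

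- Low: 0.1 × 3.4 × 0.25 × 0.3 = 0.0255, giving 2.5%
- Midpoints: 0.2 × 3.4 × 0.375 × 0.4 = 0.102, giving 9.7%
- High: 0.3 × 3.4 × 0.5 × 0.5 = 0.255, giving 22.5%

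The range for e may be too high. Section 9.2.1.2 defines routine visits as those scheduled under local standard of care, and Section 9.3.2 expects them about every 6 months. If visit timing is independent of relapse, a visit falls within 30 days of onset for about 30/182 = 16.5% of relapses, even with an EDSS at every visit. The 30 days here is only an illustrative window. Then 0.2 × 3.4 × 0.165 × 0.4 = 0.045, giving about 4.4%.

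**Effect of confirmation.** A second calculation takes 10 six-monthly visits timed independently of relapse, a relapse window w of 1 to 3 months, R of 0.1 to 0.3 and q of 30% to 60% (all assumed except the visit schedule). With p = (1 − exp(−R × w)) × q per visit:

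- at least one qualifying score: 1 − (1 − p)^10 = 2.5% to 36%
- two consecutive qualifying scores, treated as independent: 1 − (1 − p²)^9 = about 0.01% to 1.7%

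**Confirmation against exclusion.** A simulation of stable patients at EDSS 2.5, with seven half-yearly visits, an assumed score noise SD of 0.25, R = 0.2 and e = q = 50%, classed 24.5% as progressed under the written rule. Excluding relapse scores left 11.7%; requiring the rise at the next visit left 3.0%. The levels reflect values of e and q at the top of their assumed ranges. The ordering is what matters: confirmation removes more than exclusion, because it also removes rises caused by score noise.

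**The case against.** The strongest reply is that nothing here is misstated. Section 9.1.2 introduces its endpoints as examples and points to Section 9.7.5, where sustained and unconfirmed versions stand side by side under the same permissive wording. Nothing makes the unconfirmed version the lead result. Handling of EDSS scores near a relapse is commonly left to the statistical analysis plan, which is not shown. The analyses are secondary and descriptive, and no hypothesis is tested.

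Much of this stands. It is why the point is that transient deficits can be counted, not that they will be reported as progression. It does not dispose of the matter: the protocol itself sets the thresholds and chooses which endpoints to exemplify, and it leaves the version that deals with the problem optional.

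Four stronger readings are tempting, and the document does not support them:

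- **All EDSS progression results are affected.** They are not. The 6-month sustained parameters in Section 9.7.5 largely filter out transient deficits, and a rise of 1.0 does not qualify from baseline 0.
- **Section 9.7.5 contradicts Section 9.3.2.** The latter governs how relapses are recognised and counted. It sets no EDSS rule, and a relapse that leaves a lasting deficit may properly appear in both results.
- **The external comparison of progression is biased.** Section 9.7.5 says effectiveness evaluations will include external comparisons, but no EDSS comparator or comparator definition is given, so neither direction nor size can be stated. Section 9.9 says such comparisons will be discussed with their limitations.
- **About 16% of patients are misclassified.** That figure needs both e and q at the top of their assumed ranges (0.2 × 3.4 × 0.5 × 0.5 = 0.17, giving 15.6%). Midpoints give 9.7%.

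**Conclusion.** The point holds in a limited form. The EDSS endpoints exemplified in Section 9.1.2 and the abstract depend on a single unconfirmed rise, and Section 9.7.5 does not exclude scores taken during a relapse. A recovered relapse can therefore count both as a relapse and, permanently, as a first progression. The sustained versions that largely prevent this are optional.

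The size cannot be determined from the protocol. The 2.5% to 22.5% range, and the lower figure of about 4%, rest on assumed relapse rates, EDSS recording at relapse and qualifying shares; only the 3.4 years comes from the document. The consequence is possible overstatement, and too early dating, of progression in a secondary descriptive objective. The primary safety objective and the study-size calculations are untouched. The change is worth making because it costs very little.

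**What to change.** - In Section 9.1.2, the abstract and Section 9.7.5, name the proportion with, and time to, progression sustained for at least 6 months as the main EDSS endpoints, and say that they will be reported, not that they may be. Keep unconfirmed progression as supportive.
- In Section 9.7.5, state that a score obtained during a relapse neither starts nor confirms progression. Prespecify the length of the relapse window and justify it separately. It should not be taken from the 30-day rule in Section 9.3.2, which merges symptoms into one relapse and is not a recovery period.

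The cost is wording in three places and a date comparison between relapse and EDSS records, both of which are already collected. The progression estimate will be somewhat lower and later. Patients with no later EDSS cannot be confirmed, and because EDSS is recorded only when routine care produces it, their number should be reported beside the sustained result.

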9.2. Setting

9.2.1. Prospective Cohort Study in Patients With MS

9.2.1.1. Selection Criteria

Patients aged 18 and older with MS who have been newly prescribed DMF under routine clinical care are eligible to participate in the study. Efforts will be made to recruit a variety of physicians who are representative of DMF prescribers. Eligible patients must be naïve to DMF, Fumaderm[®], and compounded fumarates at the time of enrollment, but need not be naïve to other MS treatments, and must not be currently enrolled in any other clinical trial or study except for the DMF Pregnancy Registry or other studies that, according to the study Medical Director, do not conflict with this observational study (e.g., health economic studies).

Patients with previous exposure to DMF, Fumaderm[®], and compounded fumarates are excluded so as not to introduce bias; these patients may be more or less likely to experience AEs and may fail to report AEs that occurred before study enrollment. Patients participating in other clinical studies are excluded so as not to unduly confound causality assessments when a concomitant experimental agent's safety profile has yet to be established and/or the physician is blinded to the patient's treatment assignment.

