9.7.1. Analysis Population

Statistical analyses will be based on all patients who enroll in the study (defined as having an available date of informed consent) and take at least 1 dose of DMF.

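### Section 9.7.5 gives two EDSS rules that disagree for a rise from 0 to 1.0, and lists threshold outcomes as progression with no baseline condition

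*Protocol*

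**What the plan says.** All the EDSS rules stand in one bullet list in Protocol Section 9.7.5, introduced as the assessment of disability progression.

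- **Progression:** "at least a 1.0 point increase from a baseline EDSS ≥ 1.0 or at least a 1.5 point increase from a baseline EDSS = 0". It is reported as a proportion and as time to first event, and again for progression sustained for at least 6 months.
- **Thresholds:** the "proportion of patients with post-baseline EDSS values greater than certain thresholds", with ≥4.0 and >6.5 as examples, at any time and sustained for at least 6 months.
- **Three-way status (worsened, stabilized, improved):** improvement is a fall of 1.0 point or more, offered only as a definition that may be used. The middle category is given as "a stable condition as a change of ≤ 0.5 point from baseline". The category at issue here uses a single cut for every baseline: "worsening as an increase of at least 1.0 point from baseline". This outcome too has a 6-month sustained version.

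Two other sections determine who enters these proportions. Section 9.7.1 says: "Statistical analyses will be based on all patients who enroll in the study", provided they take at least one dose. Section 9.2.1.1 says: "Patients aged 18 and older with MS who have been newly prescribed DMF under routine clinical care are eligible", subject to conditions on prior fumarate exposure and other studies, but with no limit on EDSS.

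Sections 9.1 and 9.7.5 add that effectiveness will be compared with external databases, and Section 9.1 that there is no internal control cohort.

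**The concern.** The first issue is internal consistency. The protocol sets a stricter bar for progression from a baseline of 0, then drops it in the worsening category of the same list. One score at one visit can then be reported as no progression in one table and as worsening in another, and a reader of the report cannot tell which reflects the study's view of that change.

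The second issue is what the threshold proportions measure. Placed under disability progression, they will be read as the share of patients who reached a level of disability during follow-up. Without a baseline condition they also contain patients who entered at that level. The proportion then depends on baseline case mix. That matters because effectiveness is to be set against external data and no internal comparator shares the same mix. Section 9.2.2 itself foresees that prescribing habits could bring patients with more aggressive disease into the cohort.

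**Working it through.** The protocol states no numerical result or target for any EDSS outcome, so there is no figure to reproduce. The check applies the stated rules to every possible change in score.

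**Inputs.** The rules are those of Section 9.7.5. The score grid is an assumption, because the protocol does not print one: 0, 1.0, 1.5, and so on in half points to 10, which gives 20 values and 20 × 20 = 400 baseline/follow-up pairs. The progression rule fits this grid, since it provides only for baselines of 0 and of 1.0 or more. Stable is read as an absolute change of 0.5 or less.

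**Step 1: worsened against progressed.** The two labels differ for exactly one of the 400 pairs, and no pair is left unclassified.

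| Baseline → follow-up | Change | Progressed? | Three-way status |
|---|---|---|---|
| 0 → 1.0 | +1.0 | No (needs 1.5) | Worsened |
| 0 → 1.5 | +1.5 | Yes | Worsened |
| 1.0 → 2.0 | +1.0 | Yes | Worsened |
| 1.0 → 1.5 | +0.5 | No | Stable |

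Both outcomes have a sustained version, so a sustained move from 0 to 1.0 produces the same disagreement there.

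**Step 2: aligning the rules.** If worsening from 0 also needs 1.5 points, the labels agree for all pairs. But 0 → 1.0 is then neither worsened nor stable (1.0 > 0.5), so it needs a category.

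**Step 3: thresholds.** On the same grid, 13 baseline values (4.0 to 10) already satisfy ≥4.0, and 7 (7.0 to 10) already satisfy >6.5.

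- For ≥4.0 there are 13 × 13 = 169 pairs with both scores past the threshold. In 11 + 10 + … + 1 = 66 the score rises by 1.0 or more, leaving 169 − 66 = 103 pairs that are stable or improved yet counted.
- For >6.5 the figures are 7 × 7 = 49, less 5 + 4 + 3 + 2 + 1 = 15, leaving 34.

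These are counts of possible transitions, not of patients. Two examples: a patient who stays at 5.0 throughout is a ≥4.0 case, at any time and sustained; a patient who goes from 6.0 to 4.5 is improved (−1.5) and is also a ≥4.0 case.

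**Step 4: illustrative size, on assumed inputs only.**

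- *Worsened minus progressed* = share with baseline 0 × share of those who move to exactly 1.0. With 5% to 20% at baseline 0 and 10% to 30% moving: 0.05 × 0.10 = 0.5% and 0.20 × 0.30 = 6%, hence 0.5 to 6 percentage points of patients with usable scores.
- *Threshold proportion in all patients* = q × 0.9 + (1 − q) × r, where q is the share past the threshold at baseline, 90% of them stay past it, and r is the share of the rest who newly cross. With r = 5%: q = 5% gives 0.045 + 0.0475 = 9.25%; q = 30% gives 0.27 + 0.035 = 30.5%. With r = 10%: q = 5% gives 0.045 + 0.095 = 14%; q = 30% gives 0.27 + 0.07 = 34%. Among patients at risk the answer is r itself, 5% or 10%.

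**The case against.** The strongest reply is that none of this is settled. The list says what the analyses may include, the three-way categories are only definitions that may be used, and the thresholds are examples. The comments in the ENCePP checklist (Annex 2) leave the detailed analyses to a statistical analysis plan, which could align the rules and set the denominator. Progression and three-way status are also separately named outcomes, the second with a symmetric cut of 1.0 point up or down, and nothing says they must coincide. Section 9.7.5 also allows subgroup analyses by baseline EDSS, which could separate patients already past a threshold. All of this lowers the weight. It does not remove the point: the protocol does print both rules and they disagree, and it does present an unrestricted proportion as a measure of progression. The subgroup analysis is optional.

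Several stronger readings are tempting but not supported.

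- A reader might infer that the 1.5-point rule exists because 0 to 1.0 is a single step of the scale. The protocol gives no reason for the rule.
- A reader might infer that the protocol expressly counts existing disability as an outcome on treatment. It does not say so; this follows from the missing baseline condition together with Sections 9.7.1 and 9.2.1.1. As a description of prevalence the proportion is valid.
- A reader might infer that external comparison is made impossible because other sources use a customary at-risk definition. No external EDSS figure or definition is given, and the named databases are introduced for safety background rates. What stands is that case mix would confound such a comparison.
- A reader might multiply the assumed percentages by 5000. Section 9.3 records EDSS only when obtained in routine practice, so the number of patients with usable scores is unknown.
- A reader might conclude that the threshold outcomes must become Kaplan-Meier analyses. The protocol states proportions, and restricting the denominator is enough.

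**Conclusion.** Both parts hold on the text. The first is the firmer: the worsening and progression rules disagree for a rise from 0 to 1.0 and nowhere else on the assumed grid, at any time and in the sustained analyses. The second holds if Sections 9.7.5, 9.7.1 and 9.2.1.1 are followed as written: patients already past a threshold count as cases whether stable or improved, provided they stay past it, so existing and new disability are mixed and the result depends on baseline case mix.

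The size cannot be derived from the protocol, which gives no EDSS distribution. The ranges in the working rest wholly on assumed inputs and show only that the effect could be small or large. The outcomes are secondary, no formal hypothesis testing is planned (Section 9.7), and the primary safety objective is untouched. This is a worthwhile tidying of the plan, of low severity.

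**What to change.** Amend Section 9.7.5 in two places.

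1. Define worsened by the progression rule: an increase of at least 1.0 point from a baseline of 1.0 or more, or at least 1.5 points from a baseline of 0. Extend stable to include a move from 0 to 1.0, so that every transition has a category.
2. Report each threshold proportion, at any time and sustained, among patients whose baseline EDSS does not already meet that threshold. The proportion in all patients may be kept if it is labelled as prevalence.

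No new data are needed: Section 9.3.1 already collects the latest score before enrollment and, when obtained in routine practice, the score at enrollment. The cost is smaller denominators for the threshold outcomes, since patients already past the threshold, and any without a baseline score, drop out. The three-way status also loses its symmetry at the bottom of the scale: 1.0 to 0 remains an improvement while 0 to 1.0 becomes stable. A table footnote can say so.
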